#### Statistical Methods

Descriptive statistics and patients' data listings will be used in the characterization of patients' disposition, demographic and baseline characteristics, treatment exposure and safety variables. Analyses by treatment cohort and dose schedule will be provided for treatment exposure and safety variables. Additional analyses will be performed by treatment period (ie cycle 1 vs. cycles >1), if appropriate, for adverse events, and selected hematological and biochemical tests. Adverse events, hematological and biochemical toxicity will be classified according to the NCI CTCAE (version 5.0). The MedDRA (Medical Dictionary for Regulatory Activities) dictionary (version 21.0) will be used to code the reported adverse events. The anti-tumor activity will be assessed by considering the objective tumor responses defined according to the ELN recommendations for the AML population [6, 7] whereas for CMML patients the tumor response evaluation will be made according to disease specific IWG criteria [56]. All efficacy data will be documented in individual patients' data listings. Untreated patients will be identified and described separately. For the Phase II portion of the trial a futility analysis will be performed for each cohort after at least 10 evaluable patients at the same dose level are observed for at least 3 cycles (ongoing enrollment up to 10 more treated patients may continue while analysis is being performed) such that if at least one responder (i.e. one CR or CRi) is observed then the full cohort may proceed. Time-matched, replicate ECGs and PK samples will be used to explore for concentration-corrected QT interval responses. Such analyses will be further described in a separate analysis plan. For further details see Section 12.3.

Therapeutic Area:	Oncology
Product:	NMS-03592088
Indication:	Acute Myeloid Leukemia (AML) and Chronic Myelomonocytic Leukemia (CMML)
Protocol Number:	MKIA-088-001
Title of Study:	A Phase I/II Study of NMS-03592088, a FLT3, KIT and CSF1R Inhibitor, in Patients with Relapsed or Refractory AML or CMML

**Interim Analysis****CCI**Safety analysis:

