## 5.5. Phase II

Once the RP2D and schedule of NMS-03592088 have been selected and communicated to sites, the exploratory Phase II portion of the study with interim analysis for futility and safety will be opened for enrollment and will consist of two parallel cohorts:

**Cohort 1 (40 patients with a futility analysis at 10 patients):** patients with AML FLT3 Internal Tandem Duplication (ITD) mutation as assessed by central laboratory, who have failed standard of care including venetoclax and gilteritinib based therapies. Dose and schedule will be within the defined exposure cap rule defined in section 9.2.1). The enrollment in this cohort may be restricted to patients with specific prior lines/therapies and/or mutations, based on Sponsor decision.

**Cohort 2 (40 patients with a futility analysis at 10 patients):** patients with AML FLT3 Internal Tandem Duplication (ITD) mutation as assessed by central laboratory, who have failed standard of care. Dose and schedule will be within the defined exposure cap rule defined in section (refer to section 9.2.1). The cohort may be restricted to patients with specific prior lines/therapies and/or mutations, based on Sponsor decision.

The Sponsor will control the patient assignment to cohorts and may stop or pause cohorts in any phase or part of the study based on safety, efficacy or strategic reasons. The sponsor have also the possibility to explore additional phase II cohorts upon protocol amendment based on restriction of patient population and/or additional dose regimens within the described cap of exposure. The same criteria for futility analysis will apply on such cohorts.

For the FLT3-ITD mutated AML group, the main endpoint in the Phase II will be the Composite Complete Remission Rate (CRc), defined as the proportion of patients who achieved a Complete Remission (CR) or Complete Remission with Incomplete Recovery (CRi). See Section 11.2 for all details.

For the safety analysis, the rate of drug-related unacceptable toxicities and drug-related deaths will be monitored on ongoing basis using sequential boundaries.

The analyses will include all treated patients of each cohort of the Phase II portion.

All details are reported in Section 12.4.2.

For statistical considerations, see Section 12.

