## 12.2. Definition of Analyzed Study Populations

For the purpose of the analysis, the following patient populations are defined and the endpoints, to be analyzed in these populations, are specified:

- *Enrolled Patients*: This population will include all patients who are enrolled in the clinical study, regardless of whether patients receive treatment or not. This population will be evaluated in the analysis of patients' disposition.
- *Treated Patients*: The treated patient population consists of all enrolled patients who actually receive at least one treatment administration. This population will be evaluated in the analysis of patient disposition, baseline characteristics, treatment exposure, efficacy and safety.
- *Patients evaluable for determination of DLT (by dose schedule and dose level)*: for each schedule and dose level tested, this population includes all patients enrolled in dose escalation part who receive at least 70% of drug in the first cycle, unless the reason for non compliance is drug-related toxicity, and for whom a DLT assessment is available within the DLT window. In case the patient does not fulfill one or more of the aforementioned criteria, he/she will be replaced.
- *Patients evaluable for efficacy analysis (efficacy dataset)*: This is the patient population which consists of all enrolled patients in the Phase II part who are treated at the RP2D, have  $\geq 1$  on-treatment hematologic assessment(s) (i.e. they must have adequate bone marrow response evaluation). Patients who experience early death or withdrew prior to response assessment, or had technically suboptimal bone marrow sample precluding assessment, are non-evaluable for response and are excluded from the efficacy dataset. For cohort 1 and 2, only the subset of patients with FLT3-ITD mutation and no D835 and I836 mutations based on the central test will be included in this population.
- *Patients evaluable for PK analysis*: treated patients will be considered evaluable if they have sufficient baseline and on-study sampled material to provide interpretable results.

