## Appendix 2.1. Response Criteria in AML according to ELN 2022

Response Criteria in AML (2022)	
Category	Definition
Response	
Complete Remission (CR) *,†,‡	BM blasts <5%; absence of circulating blasts; NO EMD; ANC $\geq 1.0 \times 10^9/L$ (1000/ $\mu L$ ); platelet count $\geq 100 \times 10^9/L$ (100 000/ $\mu L$ )
CR with partial hematologic recovery (CRh) *,†,‡	ANC $\geq 0.5 \times 10^9/L$ (500/ $\mu L$ ) and platelet count $\geq 50 \times 10^9/L$ (50 000/ $\mu L$ ) otherwise all other CR criteria met  Comment: If CRh used, CRi should only include patients not meeting the definition of CRh
CR with incomplete hematologic recovery (CRi) *,†,‡	All CR criteria except for residual neutropenia $< 1.0 \times 10^9/L$ (1000/ $\mu L$ ) or thrombocytopenia $< 100 \times 10^9/L$ (100 000/ $\mu L$ )
Morphologic leukemia-free state (MLFS)	BM blasts <5%; absence of circulating blasts; NO EMD; NO hematologic recovery required ‡
Partial remission (PR)	Decrease of BM blast percentage to 5 to 25%; and decrease of pretreatment BM blast by at least 50%; All hematologic criteria of CR;
No response	Patient evaluable for response but not meeting the criteria for CR, CRh, CRi, MLFS or PR
Non-evaluable for response	Non-evaluable for response will include patients lacking an adequate bone marrow response evaluation. This category will include patients with early death, withdrawal prior to response assessment, or a technically suboptimal bone marrow sample precluding assessment
Progressive Disease	
Relapse	
Relapsed disease (after CR, CRh or CRi)	Bone marrow blasts $\geq 5\%$ ; or reappearance of blasts in the blood in at least 2 peripheral blood samples at least one week apart; or development of extramedullary disease

BM, bone marrow; PB, peripheral blood; ANC, absolute neutrophil count; EMD, extramedullary disease; WBC, white blood cell.

\*To recognize the potential for continuing improvements in blood counts after myelosuppressive therapy, response definitions for patients with marrow blast clearance (< 5%) may be adjusted to reflect the best hematologic response achieved prior to commencement of the next treatment cycle. Aspirate reports that include MLFS, CRh, or CRi should note the potential for post-marrow blood counts to alter the final response designation. Patients should not have received G-CSF, nor platelet transfusions within 7 days prior to hematologic response determination.

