Patients evaluable for efficacy analysis (efficacy dataset): efficacy datasets will be defined by dose level, patients receiving at least 75% of treatment at first cycle, have at least one or more on-treatment hematologic assessment(s) (i.e., they must have adequate bone marrow response evaluation), relative to ELN criteria, must have adequate baseline. Note: Patients who are not evaluable for efficacy due to early death, inadequate bone marrow sample, or withdrawal from the study prior to evaluation should be considered failures rather than non-evaluable

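### Two populations are named for Phase II efficacy, the visible text does not say which is the denominator for CRc, and one of them drops early deaths and other patients who cannot count as responders

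*Protocol*

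**What the plan says.** The Phase II primary endpoint is the CRc rate, CR plus CRi by ELN 2022 (Protocol 4.2.1, SAP 3.2.1). Protocol 5.5 describes it as a proportion of patients and does not say of which patients.

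Protocol 12.2 opens by stating that it specifies the endpoints for each population. For Treated Patients (at least one dose) it says: "This population will be evaluated in the analysis of patient disposition, baseline characteristics, treatment exposure, efficacy and safety". It then defines an efficacy dataset for Phase II: treated at the RP2D, an adequate on-treatment marrow evaluation and, for cohorts 1 and 2, FLT3-ITD without D835 or I836 by the central test. Patients with early death, withdrawal before response assessment or an unreadable marrow "are non-evaluable for response and are excluded from the efficacy dataset". No endpoint is named for this set. SAP 7 repeats both definitions, except that its mutation condition mentions only D835.

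For the US, SAP 7 has a separate definition by dose level, under which patients with the same three problems "should be considered failures rather than non-evaluable".

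Appendix 2.1 of the protocol lists non-evaluable as an ELN 2022 response category: "This category will include patients with early death, withdrawal prior to response assessment". The sections that would tie each response rate to a population (Protocol 12.3.4 and the SAP 9.7 efficacy text) are redacted.

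**The concern.** All three reasons for exclusion arise after treatment starts, and two of them, early death and early withdrawal, are often treatment failure itself. A patient who dies or stops before the first marrow is a poor outcome, yet would disappear from the rate rather than count against it.

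The trial has no control arm, so no comparison rate carries the same selection. Patients are relapsed or refractory, ECOG up to 2 is allowed, and Protocol 6.1 provides for enrolling patients whose disease is too proliferative to wait for a central result. Losing some before a marrow is plausible. What is at stake is the level of the primary CRc rate, and of the CR, CR/CRh, CR/CRh/CRi and overall response rates if they use the same set.

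**Working it through.** **Inputs.** Planned size is 40 patients per Phase II cohort (Protocol 5.5), taken here as 40 treated. Intervals are exact, two-sided 95%, as in the precision table of the Protocol Summary. The excluded share f and the number of responders x are not in the documents. I assume f = 10% to 30% and x = 4, 8 or 12.

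**The plan's own figures.** The exact limits are lower = Beta quantile 0.025 with parameters (x, n-x+1) and upper = Beta quantile 0.975 with parameters (x+1, n-x). For n = 10:

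- 1/10: 0.25 to 44.50
- 2/10: 2.52 to 55.61
- 3/10: 6.67 to 65.25

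These match the table. The half-widths come out at 22.12, 26.54 and 29.29 against the printed 22.13, 26.55 and 29.29; the differences of 0.01 are rounding. The column heading in that table counts treated patients.

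**Direction.** CR, CRh, CRi, MLFS and PR all need a marrow blast result (Appendix 2.1). A patient without an adequate marrow evaluation cannot be recorded in any of them. Excluding such patients leaves x as it is and lowers n from N to N(1-f):

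[x / (N(1-f))] / [x / N] = 1/(1-f)

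The factor is 1/0.9 = 1.11, 1/0.8 = 1.25 and 1/0.7 = 1.43 for f = 10%, 20% and 30%. It cannot fall below 1, and equals 1 only if nobody is excluded.

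**Size, N = 40 treated (rate in %, exact 95% CI):**

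| Responders | All 40 | f = 10%, n = 36 | f = 20%, n = 32 | f = 30%, n = 28 |
|---|---|---|---|---|
| 4 | 10.0 (2.8 to 23.7) | 11.1 (3.1 to 26.1) | 12.5 (3.5 to 29.0) | 14.3 (4.0 to 32.7) |
| 8 | 20.0 (9.1 to 35.6) | 22.2 (10.1 to 39.2) | 25.0 (11.5 to 43.4) | 28.6 (13.2 to 48.7) |
| 12 | 30.0 (16.6 to 46.5) | 33.3 (18.6 to 51.0) | 37.5 (21.1 to 56.3) | 42.9 (24.5 to 62.8) |

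**Which denominator applies.** The visible text points both ways.

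- For Treated Patients: 12.2 and SAP 7 assign efficacy to that population, and the precision table counts treated patients.
- For the efficacy dataset: its title, its restriction to Phase II and central FLT3-ITD (which fits the primary endpoint), SAP 9.1 and 9.2, which report patients excluded from the efficacy analysis, and the futility look, which takes place "after at least 10 evaluable patients at the same dose level are observed for at least 3 cycles".

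Nothing readable settles the matter for the final analysis.

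**The case against.** The strongest reply is that the deciding text is redacted. Protocol 12.3.4 or SAP 9.7 may name Treated Patients for the final CRc, and then this rule inflates nothing. The only visible analysis tied to evaluable patients is the futility look. That stands, and it makes the finding conditional.

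It is also fair that Phase II is called exploratory, that no null rate or success threshold for the final CRc is visible, and that SAP 9.1 reports the excluded patients with reasons, so a reader could rebuild the all-treated rate. With 8 responders and f = 10% the shift is 2.2 points, small beside an interval of 9.1 to 35.6. These points limit the consequences but do not justify an outcome-dependent denominator.

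A reader might go on to infer three things that the documents do not support.

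- **Phase II would look better than US data from the same trial.** The end of SAP 3.2 says Phase II will not start in the US before a substantial amendment. The US rule therefore covers a dose-level set, with its own 75% first-cycle requirement, and SAP 2.1 lists country-specific population definitions as an intended change. It shows that the SAP accepts the failure rule, but it is not a competing rule for the Phase II CRc.
- **Phase I has no efficacy dataset, so Phase II would look better than Phase I.** The same US definition is an efficacy dataset by dose level. Phase I also differs in dose and diagnosis, and no such comparison is planned in the visible text.
- **Appendix 2.1 contradicts 12.2.** Both classify these patients in the same way. The non-evaluable row would be empty only if best response were tabulated in the efficacy dataset, which is not shown.

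**Conclusion.** The point holds conditionally. The exclusion rule is explicit in both documents, and its direction is certain: any response rate computed on the efficacy dataset is raised by 1/(1-f). With 8 responders among 40 treated and f = 10% to 30%, 20.0% becomes 22.2% to 28.6%, a rise of 2.2 to 8.6 points. Both the responder count and f are assumptions, so the size is illustrative.

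It would be tempting to conclude that the final CRc is overstated. That is not shown, because its denominator is not visible and Treated Patients is also named for efficacy. What is shown is that the two population sections leave the choice open, although 12.2 says that it specifies it. The central-test restriction is a separate exclusion whose direction cannot be determined, and it is not part of this finding.

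**What to change.** In Protocol 12.2 and SAP 7 (non-US definition), name the denominator for the primary CRc and for CR, CR/CRh, CR/CRh/CRi and overall response, and replace the exclusion sentence:

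- Include all treated Phase II patients who meet the conditions already in the protocol definition: RP2D, FLT3-ITD positive by the central test, no D835 or I836. Align the SAP, which omits I836.
- Count early death, withdrawal before assessment and inadequate marrow as non-response, and show them in the non-evaluable row of the best-response table.
- Keep the current response-evaluable set as a labelled sensitivity analysis.

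If the redacted text already uses Treated Patients, stating so in 12.2 and SAP 7 resolves the ambiguity about which set is used.

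The cost is wording in two documents, with no extra patients or procedures. The reported rate may be somewhat lower, and a patient in true remission with an unreadable marrow would count as a failure; the sensitivity analysis shows how much that matters. The change should be made before the Phase II results are analysed.

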## 12.3. Analyses

### 12.3.1. Study Conduct and Patient Disposition

Patients' disposition and reasons for ending the treatment and the study will be presented in frequency distribution tables and individual data listings. The patients not meeting the eligibility criteria, and who are considered protocol violators as well as the ones failing to receive a complete first cycle will be identified and described by individual data listing. Reasons for stopping treatment will be summarized as frequency distribution in the treated patient population and, if clinically interesting, in other patient subsets. Untreated patients will be identified and described separately. For patients involved in the Phase II portion of the trial, all below mentioned analyses and data listings will be presented by cohort.

### 12.3.2. Baseline Characteristics

Descriptive statistics of the baseline characteristics will be generated across all treated patients. Frequency distributions will be presented for the categorical/categorized variables. Summary statistics including mean, standard deviation, median, minimum, maximum and the number of assessed patients will be calculated, as appropriate, for the quantitative variables. Individual data will be presented in listings.

### 12.3.3. Treatment Administration/Compliance

The treatment exposure and the compliance with study treatment will be descriptively analyzed in the treated patient population and, if clinically interesting, in other patient subsets. Descriptive statistics (e.g. min, max, mean, standard deviation, and median value) will be calculated on a per-patient basis for the following variables: the number of cycles administered, the overall duration of treatment, the actual and total doses administered, and the absolute and relative dose intensity. Frequency distributions of patients and/or cycles will be used to describe dose modifications, delays and omissions, as well as the reasons for deviation from the planned therapy. These data will be presented as reported in the relevant CRF sections.

### 12.3.4. Efficacy Analyses

CCI

NMS-03592088  
Protocol for Study MKIA-088-001

MKIA-088-001\_P9  
Version 9\_28 February 2024

CCI  
[Redacted text block]

[Redacted text block]

[Redacted text block]

[Redacted text block]

[Redacted text block]

[Redacted text block]

[Redacted text block]

[Redacted text block]

NMS-03592088  
Protocol for Study MKIA-088-001

MKIA-088-001\_P9  
Version 9\_28 February 2024

CCI

[REDACTED]

[REDACTED]

[REDACTED]

[REDACTED]

[REDACTED]

NMS-03592088  
Protocol for Study MKIA-088-001

MKIA-088-001\_P9  
Version 9\_28 February 2024

CCI  
[Redacted text block]

### 12.3.5. Outcomes Research Analyses

Not applicable.

### 12.3.6. Safety Analyses

CCI  
[Redacted text block]

[Redacted text block]

[Redacted text block]

[Redacted text block]

[Redacted text block]

[Redacted text block]

[Redacted text block]

### 12.3.7. Analyses of Other Endpoints

#### 12.3.7.1. Molecular Features in Biological Samples

Exploratory analyses on the relationship between molecular features and treatment efficacy variables in AML and CMML patients treated with NMS-03592088 will be performed if sufficient data are collected.

#### 12.3.7.2. Pharmacokinetics

The PK concentration population is defined as all enrolled patients treated who have at least one concentration. The PK parameter analysis population is defined as all enrolled patients treated who have at least 1 of the PK parameters of interest.

CCI

[REDACTED]

[REDACTED]

[REDACTED]

[REDACTED]

[REDACTED]

NMS-03592088  
Protocol for Study MKIA-088-001

MKIA-088-001\_P9  
Version 9\_28 February 2024

CCI  
[Redacted text block]

[Redacted text block]

[Redacted text block]

[Redacted text block]

[Redacted text block]

### 12.3.7.3. Relationship of corrected QT changes to treatment exposure

CCI  
[Redacted text block]

### 12.3.7.4. Translational Research

CCI  
[Redacted text block]

## 12.4. Interim Analysis Plan

### 12.4.1. Futility Analysis

CCI  
[Redacted text block]

NMS-03592088  
Protocol for Study MKIA-088-001

MKIA-088-001\_P9  
Version 9\_28 February 2024

CCI [REDACTED]  
[REDACTED]  
[REDACTED]  
[REDACTED]  
[REDACTED]  
[REDACTED]

[REDACTED]  
[REDACTED]  
[REDACTED]  
[REDACTED]  
[REDACTED]  
[REDACTED]

[REDACTED]  
[REDACTED]  
[REDACTED]  
[REDACTED]  
[REDACTED]

#### 12.4.2. Safety Analysis

CCI [REDACTED]  
[REDACTED]  
[REDACTED]  
[REDACTED]  
[REDACTED]  
[REDACTED]  
[REDACTED]

CCI [REDACTED]  
[REDACTED]  
[REDACTED]  
[REDACTED]  
[REDACTED]  
[REDACTED]  
[REDACTED]  
[REDACTED]  
[REDACTED]  
[REDACTED]  
[REDACTED]  
[REDACTED]

NMS-03592088  
Protocol for Study MKIA-088-001

MKIA-088-001\_P9  
Version 9\_28 February 2024

CCI  
[Redacted text block containing 7 lines of blacked-out content]

**Table 12. Safety Boundaries for Toxicity Monitoring**

CCI

Empirical stopping rules for drug-related toxicities and drug-related deaths, will be applied to first 24, 27, 30 and 36 patients. The enrollment will be stopped if the numbers of patients who experience toxicity occur as follows: 8 out of first 24, 9 out of the first 27, 12 of the first 36.

Note: These rules are based on a per patient count, not the absolute number of events experienced by an individual patient. No single patient can count more than once toward these safety rules.

### 12.5. Data Monitoring Committee

An Official Independent Data Monitoring Committee is not foreseen. Regular teleconferences will be organized between the Investigators and the Sponsor to strictly review all relevant safety issue (e.g., grade 3-4 clinical and laboratory events, drug-related Serious Adverse Events and Deaths) and take decision on the dose escalation, where applicable (as also mentioned in Section 5.2 Dose Escalation).

### **13. END OF THE TRIAL**

For the purpose of this study, the end of the trial is defined as the date of the last visit of the last patient, including follow up.

### **14. QUALITY CONTROL AND QUALITY ASSURANCE**

The Sponsor assumes accountability for actions delegated to other individuals (e.g., Contract Research Organizations).

Study monitors will perform ongoing source data verification to confirm that data entered into the eCRF by authorized site personnel are accurate, complete, and verifiable from source documents; that the safety and rights of participants are being protected; and that the study is being conducted in accordance with the currently approved protocol and any other study agreements, ICH GCP, and all applicable regulatory requirements.

The Investigator must permit study-related monitoring, audits performed by the Sponsor or designee, IRB/IEC review, and regulatory agency inspections and provide direct access to source data documents.

It is important that the Investigator and his/her relevant personnel are available during the monitoring visits and possible audits or inspections and that sufficient time is devoted to the process.

The sponsor or designee is responsible for the data management of the study including quality checking of the data. That means that following data entry or electronic receipt of data, data validation will take place and Forms/Reports for data clarifications will be addressed to the Investigator. Data management activities will address the coding and review of terms by scientific and clinically qualified staff.

